10.5 Taper Period (Phone calls* 1-2)

1. Perform a brief interview and history interval.
2. Complete the phone check-in form.

3. Record any new medical problems and general tolerability.
4. Record changes to concomitant medications and review dosing compliance.
5. Provide information on the next dose of the drug, according to the tapering schedule.

The taper period will occur over a three-week period according to the following scheme:

Study drug (ezogabine)
750 mg orally daily for 1 week
600 mg orally daily for 1 week
300 mg orally daily for 1 week
Discontinue

Subjects who are not able to tolerate the 900mg daily dose will follow one of the below taper schedules depending on the maximally tolerable dose.

Case 1. Patient is taking 750 mg/daily at primary outcome visit: 2-week taper

Study drug (ezogabine) – 750 mg
600 mg orally daily for 1 week
300 mg orally daily for 1 week
Discontinue

In Case 1, subjects will be contacted by a research coordinator for Visits 6 and 7 during the first and second weeks of the taper period, respectively.

Case 2. Patient is taking 600 mg/daily at primary outcome visit: 1-week taper

Study drug (ezogabine) – 600 mg
300 mg orally daily for 1 week
Discontinue

In Case 2, subjects will be contacted by a research coordinator for Visit 6 during the first week of the taper period. The Visit 7 telephone call will not take place as the Study Exit Visit will be scheduled after the subject completes their first week of the medication taper.

Case 3. Patient is taking 450 mg/daily at primary outcome visit: 1-week taper

Study drug (ezogabine) – 450 mg
300 mg orally daily for 1 week
Discontinue

In Case 3, subjects will be contacted by a research coordinator for Visit 6 during the first week of the taper period. The Visit 7 telephone call will not take place as the Study Exit Visit will be scheduled after the subject completes their first week of the medication taper

Case 4. Patient is taking 300 mg/daily at primary outcome visit: No additional taper needed

In Case 4, subjects who are taking a maximum daily dose of 300mg will not require further taper before ending study drug intake. In these cases, subjects will not undergo a taper period and/or complete a Visit 6 or Visit 7 telephone call. The study exit visit will be scheduled after completion of the the Primary Outcome Visit (V5).

** The weekly phone calls during taper period (i.e. Visit 6 and Visit 7) will be conducted by a study research coordinator. The weekly phone calls will be scheduled one and two weeks after the Primary outcome visit (Visit 5), respectively. However, to ensure feasibility of the study and participants' availability, weekly phone calls may occur within 3 days before or after the scheduled one. If patients follow a one- or two-week taper period, one or two weekly phone calls will be scheduled respectively. An explicit request by the study participants or any safety concern (e.g., new and unexpected adverse effects, increased suicidality risk) will trigger a follow up phone call assessment by a study physician. At physician's discretion, an in-person visit will be scheduled.*

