5.3 Safety Evaluations

Safety will be monitored by the evaluation of potential adverse events, clinical laboratory test results, vital signs measurements, physical examination, ECG and ophthalmological findings. Our safety evaluations include frequency and severity of observed adverse events over the study treatment period. The frequency and severity of adverse events will be compared between the treatment conditions. For a complete discuss of risks associated with the study drug, please see section 2.1 “Risk/Benefit Assessment”. For a complete discussion of study procedures, please see section 9 “Study Procedures and Guidelines”. Below, we outline specific safety evaluations conducted as part of the study protocol.

Monitoring for Worsening Depression and Suicidal Ideations or Behaviors

Participants will meet with a study clinician weekly during the treatment period. The interval medical history will be obtained and adverse events, changes to concomitant medications and dosing compliance will be recorded. Suicidal ideation and behavior will be specifically assessed, including a review of the Columbia Suicide Severity Rating Scale (C-SSRS) and the overall severity of symptoms will be monitored by the clinical global impression scale (CGI-S). If, at any point during the clinical trial, a participant will be assessed with a suicidal ideation with any intent or plan, as measured by a C-SSRS score of greater than 3 during the past week and/or with a CGI-S score ≥ 6 (indicating extreme illness severity) or a CGI-I score ≥ 6 (indicating an extreme worseness of the symptoms), the site PI, or his designee, will conduct a safety review to determine the appropriate course of action including whether acute intervention is needed and whether it is in the best interests of the subject to continue in the study.

Safety review: The safety review will consist of a separate review of safety and well-being of the participant by the site PI or his designee. This review will be documented by a Safety Review Form (SRF) that will be filed in the subject binder and that will consist of a brief description of the case and of the event that triggered the review. Outcome of the review will be the decision whether to continue or discontinue the subject from the protocol (if

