1.2.1 Study duration and time points

Participants will be followed for up to 14 weeks. The screening period may last up to 6 weeks; after randomization, titration and treatment lasts 5 weeks at which point the primary endpoint is ascertained. Participants will continue to be followed for a 3 week medication taper period after collection of the primary endpoint.

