4. SAFETY ENDPOINTS

The incidence and frequency of all anticipated and unanticipated serious and non-serious adverse events (AEs) that occur between randomization and study exit (V8) eight weeks after randomization will be determined. Severity/grade and expectedness will be assessed by the study clinician. The Medical Dictionary for Regulatory Activities (MedDRA) system organ class and preferred terms will be recorded for each reported AE.

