5.5 Safety Analysis

All adverse events in this study will be analyzed from the time of randomization. All adverse events will be analyzed using the ITT population.

AEs will be mapped to the MedDRA coding system. The incidence of non-serious AEs and serious AEs will be summarized by System Organ Class, MedDRA Preferred Term and treatment.

The number and percentage of patients with an AE or serious AE will be presented. For the incidence count, a patient will be counted only once for a specific MedDRA Preferred Term, although a MedDRA Preferred Term might be recorded more than once for a particular patient.

The number and rate of each AE will also be presented. Differences in the incidence of individual AEs will be assessed using negative binomial regression with the treatment group as the predictor.

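### Post-V5 adverse-event contacts and exit timing depend on the dose tolerated, which conflicts with the SAP's single eight-week window and may modestly bias unadjusted AE comparisons toward no difference

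*Protocol*

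**What the plan says.** **Schedule after V5.** Protocol 10.5 makes it depend on the dose at V5:

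- 900 mg: three-week taper, with calls one and two weeks after V5.
- 750 mg: two-week taper and two calls; no exit time is stated.
- 600 or 450 mg: one-week taper and one call. "The Visit 7 telephone call will not take place as the Study Exit Visit will be scheduled after the subject completes their first week" of taper.
- 300 mg: "In these cases, subjects will not undergo a taper period and/or complete a Visit 6 or Visit 7 telephone call". Exit follows V5, with no interval given.

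The footnote to 10.5 adds: "If patients follow a one- or two-week taper period, one or two weekly phone calls will be scheduled respectively". Sections 10 and 10.6 and the Table 2 footnote cap the exit visit at six weeks after V5, whatever the dose.

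**Window in the SAP.** SAP 1.2.1 says that "after randomization, titration and treatment lasts 5 weeks at which point the primary endpoint is ascertained", and then: "Participants will continue to be followed for a 3 week medication taper period after collection of the primary endpoint". SAP 4 covers AEs "that occur between randomization and study exit (V8) eight weeks after randomization will be determined". Protocol 12.1 and 12.2 label the exit visit Day 57.

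**Comparison.** Protocol 5.3 states: "The frequency and severity of adverse events will be compared between the treatment conditions". SAP 5.5 states: "The number and percentage of patients with an AE or serious AE will be presented", with each patient counted once per Preferred Term. It tests individual AEs with a negative binomial model that has treatment as predictor and no stated offset. SAP 5.1 also defines event rates as events over patient-time, up to each patient's own exit.

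**The concern.** How long and how often a participant is asked about AEs after V5 is decided by how well that participant tolerated the drug, which is itself a safety outcome. The rule is the same in both arms and operates under the blind, but that does not equalise follow-up if intolerance differs by arm. A difference is plausible: Protocol 1.2 gives dizziness, drowsiness and fatigue on ezogabine as 23%, 22% and 15%, and Protocol 8.4.1 lets participants be held at a lower dose for tolerability. The least tolerant participants would then have the shortest scheduled observation.

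The secondary safety objective (Protocol 3.2) and the between-arm AE comparison are at stake. So is a plain inconsistency: the SAP describes one window and the protocol's schedule produces several.

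**Working it through.** **1. The plan's own figure.** Five weeks to V5 plus a three-week taper is 5 + 3 = 8 weeks. Day 57 gives (57 − 1)/7 = 8.0 weeks. The SAP's eight weeks reproduces, for the full-dose schedule only.

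**2. Nominal windows by dose at V5** (V5 at week 5; window = 5 + taper weeks)

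| Dose at V5 | Taper (weeks) | Nominal window (weeks) | Share of 8 |
|---|---|---|---|
| 900 mg | 3 | 8 | 100% |
| 750 mg | 2 | 7 (inferred) | 87.5% |
| 600 or 450 mg | 1 | 6 | 75% |
| 300 mg | 0 | about 5 | 62.5% |

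These are nominal. With V5 at week 5, the cap allows exit as late as week 5 + 6 = 11 at any dose. Participants exited early for continuing intolerance (Protocol 8.4.1) can have less than 5 weeks.

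**3. Percentage of patients with a given AE.** The documents give no dose-limited share, so these are assumptions: a share q of 10% to 40% on ezogabine, 0% on placebo, and 1 to 3 weeks lost (L).

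- Mean ezogabine window = 8 − qL: from 8 − 0.1 × 1 = 7.9 to 8 − 0.4 × 3 = 6.8 weeks (about 1% to 15% shorter).
- For an event with eight-week risk R and constant hazard, λ = −ln(1 − R)/8, and the observed risk is (1 − q)R + q[1 − exp(−λ(8 − L))].
- R = 23%, q = 10%, L = 1: observed 22.74%, a loss of 0.26 points, or 0.06 of 24 patients.
- R = 23%, q = 40%, L = 3: observed 19.83%, a loss of 3.17 points, or 0.76 of 24 patients.
- R = 15%, same two extremes: losses of 0.17 and 2.14 points, or 0.04 and 0.51 of 24 patients.

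**4. Rates and counts.** Assume ezogabine 0.05 events/week before V5, placebo 0.025/week throughout, 30% of ezogabine participants losing 3 weeks, and none on placebo. Mean ezogabine time is 8 − 0.3 × 3 = 7.1 weeks. Placebo has 8 × 0.025 = 0.20 events per patient. With b the ezogabine rate after V5, true events are 5 × 0.05 + 3b and observed events are that total minus 0.9b.

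| Ezogabine rate after V5 | True events | Observed events | True ratio | Patient-time rate ratio | Count ratio, no offset |
|---|---|---|---|---|---|
| Unchanged, 0.05 | 0.400 | 0.355 | 2.00 | 2.00 | 1.78 |
| Halved, 0.025 | 0.325 | 0.3025 | 1.63 | 1.70 | 1.51 |
| Doubled, 0.10 | 0.550 | 0.460 | 2.75 | 2.59 | 2.30 |

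The count ratio without an offset shrinks in all three rows. The patient-time rate ratio is right in the first, too large in the second and too small in the third.

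**The case against.** The case against has several parts, and much of it stands.

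- *The windows are not fixed.* A reader might infer that dose-limited participants get exactly 5 to 7 weeks. The documents do not say so: the six-week cap applies at every dose, and the 750 mg and 300 mg cases state no exit time. But a ceiling does not make windows equal, so the conflict with the SAP remains.
- *The missing weeks are not the taper.* A reader might infer that dose-reduction events go unseen. At 600 or 450 mg, exit follows completion of the one-week taper. What is missing against eight weeks is mostly off-drug time.
- *Patient-time rates.* A reader might infer that these shrink too. Under a constant hazard they do not, and they overstate the difference if ezogabine events cluster before V5. Protocol 2.1 says dizziness and somnolence usually arise during titration.
- *The dose-limiting event is normally already counted.* This stands. Only new terms or later events can be lost.
- *A larger effect.* Assume 30% of ezogabine and 5% of placebo participants observed for one of the three post-V5 weeks, with true post-V5 risks of 20% and 10%. The difference then falls from 10 to 6.5 points. That covers post-V5 events alone, whereas the plan counts from randomisation.
- *Tolerability.* Protocol 1.2 reports good tolerability and no discontinuations in a pilot of nine, so the dose-limited share may be low.
- *Existing safeguards.* Physician calls in the taper period need a request or a safety concern, and follow-up after exit covers events present at exit. Neither collects new events systematically.

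**Conclusion.** The point holds in a limited form. Contacts and nominal exit after V5 depend on a post-randomisation tolerability outcome, and this contradicts SAP 1.2.1, SAP 4 and the Day 57 label. If intolerance is commoner on ezogabine, which is a reasonable inference without a figure behind it, two planned measures lean modestly toward no difference for new events after V5: the percentage of patients with an AE, and negative binomial counts if no offset is used. Patient-time rates have no bias of fixed direction.

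The size is small: at most 0.76 of 24 patients per common term, under constant hazard with up to 40% of ezogabine and no placebo participants dose-limited.

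A reader might also infer that the go/no-go decision is affected, because Protocol 3.1 makes acceptable tolerability a condition. The documents do not support that: SAP 3.1 makes the primary endpoint the only criterion, and Protocol 16 gives the SAP precedence for analyses.

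**What to change.** **Protocol.** Define one AE-ascertainment window for every randomised participant, from randomisation to week 8, whatever the dose at V5 and whether or not drug is still taken. With V5 at week 5 this is three weeks after V5. Fill it with the existing phone check-in form 1, 2 and 3 weeks after V5 where no visit falls then, and seek the same contact to week 8 from those who exit early. Leave the timing of the exit ECG, laboratory tests and eye examination as it is.

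**SAP 4 and 5.5.** Compare AEs over this window, name log patient-time as the offset in the negative binomial model, and report AEs up to V5 and after V5 separately. V5 can slip to week 6, so state that the window is anchored at randomisation.

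**Reconcile.** Protocol 10.5, 10.6, 12.1, 12.2 and the Table 2 footnote need to agree with SAP 1.2.1 and 4. The exit visit is called Visit 6 in 10.6 and V8 in Section 10, Table 2 and SAP 4, while 10.5 uses Visit 6 for a phone call. Protocol 2.1 describes withdrawal over three weeks or more, barring safety concerns, and 10.5 has shorter tapers; these must be reconciled too. No view is taken on the taper schedule.

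**Cost.** Wording changes, plus short calls: about one extra at 750 mg, two at 600 or 450 mg and three at 300 mg, with similar contact for early exits. AE follow-up lasts up to about three weeks longer for dose-limited participants who reach V5, and longer for those who exit before it.

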10.6 Study exit Visit (Visit 6) and early withdrawal

1. Perform a clinical interview and history interval
2. Record any AEs.
3. Record changes to concomitant medications and review subject diary for adverse experiences and dosing compliance.
4. Perform a physical examination with recording of vital signs
5. Perform EKG.
6. Perform an ophthalmological exam.
7. Collect blood for clinical laboratory tests
8. Collect urine for urinalysis, urine toxicology and pregnancy test (applies to women of child-bearing potential only).
9. Perform self and clinician administered ratings scale:
 - SHAPS
 - TEPS

- ACIPS
- SLIPS
- QIDS-SR
- MADRS
- CSSRS
- CGI-S
- CGI-I

10. PRT*.

11. Structural MRI, fMRI during IFT, resting state connectivity*

Note: The exit visit may occur on up to three separate days, within 6 weeks of the Primary Outcome Visit (Visit 5). The subject will be considered exited from the study when all the procedures listed above will be completed.

** This procedure will be performed ONLY for early withdrawal visits that take place before completion of the primary outcome visit. Capturing outcome data for patients who do not complete the full study protocol will allow a more precise estimate of the treatment effect.*

Provision of study follow-up for treatment emergent adverse events at study exit: in case of any adverse event (including, but not limited to suicidal ideation or behavior) present at the study exit visit, subject will be referred to follow-up care until the event is resolved and/or a stable care plan is in place. The site PI will follow up with the subject until the abnormal parameter or symptom has resolved or stabilized.

11 ADVERSE EXPERIENCE REPORTING AND DOCUMENTATION

11.1 Adverse Event

An Adverse Event (AE) is any untoward medical occurrence in a study subject administered an investigational product and that does not necessarily have a causal relationship with this treatment.

An AE therefore can be any unfavorable and unintended sign (including laboratory finding), symptom or disease temporally associated with participation in an investigational study, whether or not considered drug-related. In addition to new events, any increase in the severity or frequency of a pre-existing condition that occurs after the subject signs a consent form for participation is considered an AE. This includes any side effect, injury, toxicity, or sensitivity reaction.

Any condition, laboratory abnormality, or physical finding with an onset date prior to the subject signing consent for study participation is considered to be pre-existing in nature and part of the subject's medical history and will not be recorded as AEs.

AE Expectedness

An unexpected AE is any adverse drug event, the specificity or severity of which is not consistent with the current IB or prescribing information for a marketed compound. Also, reports which add significant information on specificity or severity of a known, already documented AE constitute unexpected AEs. For example, an event more specific or more severe than described in the IB would be considered “unexpected”.

AE Severity

Adverse events will be summarized by the Medical Dictionary for Regulatory Activities (MedDRA) system organ class and preferred terms. Separate tabulations and listings will be produced for related adverse events, serious adverse events, discontinuation due to adverse events and events of at least grade 3 severity.

List criteria for AEs according to the Medical Dictionary for Regulatory Activities (MedDRA) Version 19.0 (March 2016) should be used to assess and grade AE severity, including laboratory abnormalities judged to be clinically significant. If the experience is not covered in the abovementioned criteria, the guidelines shown in Table 3 below should be used to grade severity. Notably, the term “severe” is a measure of intensity and that a severe AE is not necessarily serious.

Table 3. AE Severity Grading

Severity (Toxicity Grade)	Description
Mild (1)	Transient or mild discomfort; no limitation in activity; no medical intervention or therapy required. The subject may be aware of the sign or symptom but tolerates it reasonably well.
Moderate (2)	Mild to moderate limitation in activity, no or minimal medical intervention/therapy required.
Severe (3)	Marked limitation in activity, medical intervention/therapy required, hospitalizations possible.
Life-threatening (4)	The subject is at risk of death due to the adverse experience as it occurred. This does not refer to an experience that hypothetically might have caused death if it were more severe.

AE Relationship to Study Drug

The relationship of an AE to the study drug should be assessed using the following the guidelines in Table 4.

Table 4. AE Relationship to Study Drug

Relationship to Drug	Comment

Definitely	Previously known toxicity of agent; or an event that follows a reasonable temporal sequence from administration of the drug; that follows a known or expected response pattern to the suspected drug; that is confirmed by stopping or reducing the dosage of the drug; and that is not explained by any other reasonable hypothesis.
Probably	An event that follows a reasonable temporal sequence from administration of the drug; that follows a known or expected response pattern to the suspected drug; that is confirmed by stopping or reducing the dosage of the drug; and that is unlikely to be explained by the known characteristics of the subject's clinical state or by other interventions.
Possibly	An event that follows a reasonable temporal sequence from administration of the drug; that follows a known or expected response pattern to that suspected drug; but that could readily have been produced by a number of other factors.
Unrelated	An event that can be determined with certainty to have no relationship to the study drug.

11.2 Serious Adverse Events (SAE)

An SAE is defined as any AE occurring at any dose that results in any of the following outcomes:

- Death
- Life threatening experience defined as any adverse experience that places the subject, in the view of the treating physician, at immediate risk of death at the time of occurrence; i.e, it does not include a reaction that, had it occurred in a more severe form, might have caused death.
- Requires inpatient hospitalization or prolongation of an existing hospitalization (except scheduled hospitalizations for non-acute, unrelated cause such as an elective surgery)
- Results in persistent or significant disability/incapacity
- Is a congenital anomaly/birth defect in the offspring of an exposed subject
- Important medical events that may not result in death, be life threatening, or require hospitalization, may be considered an SAE when, based upon appropriate medical judgment, it jeopardizes the subject and may require medical or surgical intervention to prevent one of the outcomes listed in this definition.
- Any death occurring within 30 days of the subject receiving study drug, regardless of the subject having discontinued from the protocol, must be reported as an SAE.

Other important medical events may also be considered an SAE when, based on appropriate medical judgment, they jeopardize the subject or require intervention to prevent one of the outcomes listed.

11.2.1 AE/SAE Reporting Procedures

To local PPHS (IRB) and Sponsor (e.g., Study PI, [name])

AEs are reportable to the IRB and to the Study PI ([name]) within 5 business days *when they meet the following definition:*

Any harm experienced by a subject or other individual that in the opinion of the investigator is *unexpected AND at least probably related* to the research

A harm is *at least probably related* to the research if in the opinion of the investigator the research procedures more likely than not caused the harm

All AE/SAEs with an onset date after the subject signs consent for study participation must be reported to the IRB at the time of annual renewal. Details of the event must include severity, relationship to study drug, duration, action taken, and outcome.

All AE/SAEs that are considered related to study drug must be followed to resolution or stabilization if improvement is not expected. AE/SAEs that completely resolve and then recur should be recorded as a new AE/SAE. AE/SAEs that are considered related to study drug and continuing at 30 days post-last dose should have a comment in the source documents by the site PI that the event has stabilized or is not expected to improve.

To NIMH DSMB

All AEs and SAEs will be reported to the NIMH DSMB in data reports prepared three times annually. Details of the event must include the AE, severity, expectedness, relationship to study drug, duration (start/ stop date), action taken, and outcome. In addition, SAEs that meet the following definition are considered immediately reportable SAEs and will be reported to the NIH DSMB within **3 business days** of the site PI awareness of the event:

- All deaths and immediately life-threatening events, whether related or unrelated;
- SAEs that are unexpected and at least probably related;
- SAEs that are expected or unrelated, and are not deaths or immediately life threatening (i.e., suicide attempts), will be reported to the DSMB/NIMH in the tri-annual report.

All AE/SAEs that are considered related to study drug must be followed to resolution or stabilization, if improvement is not expected. AE/SAEs that completely resolve and then recur should be recorded as a new AE/SAE. AE/SAEs that are considered related to study drug and continuing at 30 days post-last dose should have a comment in the source documents by the PI that the event has stabilized or is not expected to improve. Other supporting documentation of the event may be requested by the DSMB/NIMH and should be provided as soon as possible.

To FDA

A report on the MedWatch 3500A form must be sent to the FDA when the event is:

- (1) serious, unexpected suspected reaction (the investigator judges there is evidence to suggest a causal relationship);
- (2) findings from other clinical, animal, or in-vitro studies that suggest significant human risk and
- (3) a clinically important increase in the rate of a serious suspected adverse reaction no later than 15 days after determining that the information qualifies for reporting.

Unexpected fatal or life-threatening suspected SAEs should be reported no later than 7 calendar days after initial receipt of the information.

Pregnancy

Subjects will be asked to immediately inform the study team and her doctor if any of the following occur:

- She becomes pregnant while taking the study drug
- She misses her menstrual period, or experiences unusual menstrual bleeding
- She stops using birth control
- She thinks, FOR ANY REASON, that she may be pregnant

Pregnancies occurring while the subject is participating in the study or within 30 days after the subject's administration of study drug are considered expedited reportable events. Ezogabine is to be discontinued immediately and the subject instructed to return any drug to the Investigator. The pregnancy will be considered an immediately reportable event and will be reported to the DSMB and the study PI/Sponsor within 3 business days of the site PI becoming aware of the event. The event will also reported to the site local IRB within 5 business days or following the local IRB regulations, whichever is more conservative.

According to the ezogabine packaging information, physicians are advised to recommend that pregnant patients who took ezogabine enroll in the North American Antiepileptic Drug (NAAED) Pregnancy Registry. This can be done by calling the toll-free number [name], and must be done by patients themselves. Information on the registry can also be found at the website www.aedpregnancyregistry.org.

Suicidality

The careful monitoring of suicidal ideation (SI) and suicidal behavior is a critical component of any study conducted in patients with MDD as treatment emergent suicidal ideation has been associated with the use of antidepressants and other drugs with CNS penetration. A study clinician assesses SI, suicidal behavior, and risk at each study visit and a CSSRS is completed.

If, at any point during the clinical trial, a participant will be assessed with a suicidal ideation with any intent or plan, as measured by a C-SSRS score of greater than 3 during the past week and/or with a GCI-S score ≥ 6 (indicating extreme illness severity) or a CGI-I score ≥ 6 (indicating an extreme worseness of the symptoms), the site PI, or his designee, will

conduct a safety review to determine the appropriate course of action including whether acute intervention is needed and whether it is in the best interests of the subject to continue in the study. For more information refer to section 2.1 “Risk/Benefit Assessment” and 5.3 “Safety evaluations.”

